## Data Abstraction

### **Health Research Record Request (R3)**

The Health Research Record Request (R3) team is a single point-of-contact for researchers to request access to components of UPMC-based electronic medical records for research purposes. The GDM2 Study will work with the R3 team to facilitate data abstraction for independent outcome variables and covariates from the participants' maternal and neonatal EMR. The research team will follow-up with the entire maternal and infant pair cohort with the assistance of the R3 team. Variables will be selected and requested by the PI.

### *R3 Data Collection*

Once written consent is provided and the participant completes the first study visit, at least one prenatal and two postpartum EHR data abstractions of their records will be conducted. R3 staff will abstract information at various time points of the GDM2 Study. The following data will be collected:

- General demographic information will be collected, including maternal age, race, and type of insurance coverage
- Pre-pregnancy weight; all measured prenatal weights; pregnancy-induced hypertension and associated gestational age; delivery or postpartum weight; and last recorded weight prior to pregnancy
- Obstetric history and medical history including type of contraception, medications and medical diagnoses at baseline and delivery, as well as blood pressures at time of delivery
- Last menstrual period before pregnancy; patient-reported pre-pregnancy weight at the first prenatal visit; type of delivery; prenatal and delivery complications
- Number of cigarettes before pregnancy and at each trimester; quantity and frequency of alcohol and drug use
- Information regarding any treatment for gestational diabetes – we will ascertain the existence of GDM treatment including any of the following: medical nutritional therapy; self-monitoring of glucose; insulin therapy with initial dose, dose at delivery, and total maximum dosage; or oral hypoglycemic agents such as glyburide or metformin with initial dose; dose at delivery, and total maximum dosage
- Number of ultrasounds and tests for assessment of fetal wellbeing (biophysical profiles, non-stress tests), date of delivery, and gestational age at delivery
- Information regarding neonatal course, including need for NICU or special care nursery admission; need for intubation or additional respiratory support as well as duration of

such support; hypoglycemia (defined as blood glucose <40 mg/dL in the first 24 hours of life); and hyperbilirubinemia requiring phototherapy, will also be collected

- Labs, diagnostic imaging/tests, and medical history (e.g., height, weight, blood pressure, and diagnoses) from the outpatient, ED, and inpatient record on the maternal and infant pair cohort

NOTE: The EHR also enables the retrieval of clinical and administrative data from certain other area hospitals in the event that women delivery or present to the emergency department at a hospital other than MWH, through the use of “Care Everywhere”.

### *Data Collection Associated with Study Outcomes*

To assess the study’s main outcomes, data abstraction through the R3 system will collect the following data:

- Small for gestational age (SGA, defined as birth weight  $\leq 10^{\text{th}}$  percentile for gestational age) or large for gestational age (LGA, defined as birth weight  $\geq 90^{\text{th}}$  percentile for gestational age): assessed using the birth weight and gestational age from the delivery record (SGA and LGA will be defined using sex-specific U.S. birth weight curves corrected for implausible ultrasound estimates (Talgi N, et al., *Pediatrics* 2014). Macrosomia will be defined in two ways: birth weight  $\geq 4000$  grams and birth weight  $\geq 4500$  grams.
- Cesarean delivery: defined as either primary or repeat C-section. We will also include information on the primary indication for the C-section, including prior C-section with no TOLAC (trial of labor after C-section), failure to progress, fetal intolerance to labor, breech presentation, placenta previa or other placental abnormalities, and other.
- Fetal growth and body composition measured using length and weight
- Maternal composite: (1) 3rd or 4th degree vaginal lacerations; (2) postpartum hemorrhage (defined as an estimated blood loss >1000 mL after vaginal delivery or >1500 mL after C-section, with or without need for blood transfusion); (3) pre-eclampsia and hypertensive disorders or pregnancy (defined according to ACOG diagnostic criteria) – will be obtained from the delivery and ICD-9 and -10 diagnostic codes in the EHR
- Neonatal composite: (1) hypoglycemia (defined as blood glucose <40 mg/dL in the first 24 hours of life, measured by heel stick within 1 hour after delivery); (2) hyperbilirubinemia requiring phototherapy (bilirubin measured transcutaneously from 36 hours post-delivery and as needed); (3) stillbirth (absence of fetal heart tones before delivery); (4) birth trauma (defined as shoulder dystocia or brachial plexus injuries) – will be obtained from the lab section of the neonatal EHR

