### **3, 6, and 9 Month Postpartum Forms**

The following forms are to be completed at the 3, 6, and 9 month postpartum time points:

- **Health Outcomes Form:** This form queries participants about visits to the emergency department, hospitalizations, contraception, pregnancy, or any new information regarding their and their baby’s health.
- **Infant Feeding Questionnaire:** This form captures basic information regarding breastfeeding, formula feeding, and solid food feeding. The form also captures the infant’s height, weight, and general health in the previous 3 months.

The following forms will be used on an *as needed* basis at the 3, 6, and 9 month postpartum time points:

- Protocol Deviation Form: This form is used in the event of a protocol deviation, including but not limited to a breach of confidentiality.
- Infant Status Form: This form is used to document any notable changes in the infant's status or custody situation (e.g., death, adoption, loss of custody, hospitalization, etc.)
- Withdrawal and Termination Form: The withdrawal and termination form is used when the participant is no longer interested in participation, is lost to follow-up, or can no longer participate in the study.

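### The neonatal composite counts stillbirth but not death after live birth, so on the usual any-component reading a live-born infant who dies without another component counts as having no event

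*Protocol*

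**What the plan says.** The composite is defined in the protocol under Data Collection Associated with Study Outcomes, among the data meant to assess the main outcomes. It is a closed, numbered list.

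- Component 1 is "hypoglycemia (defined as blood glucose <40 mg/dL in the first 24 hours of life, measured by heel stick within 1 hour after delivery".
- Component 2 is "2) hyperbilirubinemia requiring phototherapy (bilirubin measured transcutaneously from 36 hours post-delivery and as needed".
- Components 3 and 4 are "3) stillbirth (absence of fetal heart tones before delivery); (4) birth trauma (defined as shoulder dystocia or brachial plexus injuries".

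Death of a live-born infant is not on the list. The general abstraction list under R3 Data Collection covers "Information regarding neonatal course, including need for NICU or special care nursery admission; need for intubation or additional respiratory support", then hypoglycemia and hyperbilirubinemia. It does not name death, although it also takes in infant diagnoses from inpatient and other records.

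Infant death after birth is named only as an example on the Infant Status Form, which records changes in the infant's status or "custody situation (e.g., death, adoption, loss of custody, hospitalization, etc". That form is completed as needed at the 3, 6 and 9 month calls and at Visit 3. Under Postpartum Telephone Encounters, those contacts are limited to participants with GDM, those designated mild GDM and a random group without GDM. Death also appears as a general example of a serious adverse event, with no link to the composite.

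**The concern.** By including stillbirth, the composite treats death as part of what it measures. It then draws the line at delivery: a death shortly before birth is an event, and a death shortly after birth is not unless another component occurred first. Nothing in the protocol explains that boundary.

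The omission also interacts with the other components. Death ends the period in which they can be observed, and the bilirubin component is affected most because it is assessed mainly from 36 hours. An infant who dies on the first day can therefore end up in the same category as a healthy one.

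What is at stake is what the endpoint means. A reader of the trial report would take a lower composite rate to mean better neonatal outcomes, while the gravest of them may sit on the favorable side.

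**Working it through.** The protocol states no figure on this point. It gives no composite event rate, effect size, alpha or power, so no effect of the omission on power can be recomputed. The check has two parts.

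**1. Reading the definition against the time of death** (any component present = event)

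- Death before delivery: the stillbirth component is met, so this is an event.
- Death after live birth but before the heel-stick glucose, which is due within 1 hour: the glucose may be missing and bilirubin has not been measured. Birth trauma can still be recorded. This is an event only if birth trauma (or a low glucose, if taken) is present.
- Death after the glucose test but before about 36 hours: hypoglycemia and birth trauma could have been recorded. Bilirubin counts only if it was measured early because it was needed and phototherapy was required.
- Death later than that: all the other components could have been met, but the death itself still adds nothing.

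In the last three cases an infant with no other component has no event.

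**2. Scale**

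Inputs:
- N = 920, the recruitment goal (Recruitment Plan).
- Attrition of about 15% (Study Withdrawal and Termination), which leaves 920 × (1 − 0.15) = 782.
- Neonatal death rate r: not in the protocol. I assume 0.5 to 5 per 1,000 live births, for scale only.

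Expected deaths = N × r:
- 920 × 0.0005 = 0.46; 920 × 0.005 = 4.6
- 782 × 0.0005 = 0.39; 782 × 0.005 = 3.91

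Probability of at least one death = 1 − (1 − r)^N:
- N = 920: 0.37 to 0.99
- N = 782: 0.32 to 0.98

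Rise in the composite rate if death were added: it cannot exceed r, so at most 0.005, or 0.5 percentage points. If death were independent of the other components, the rise would be r × (1 − p), with p the composite rate without death. For assumed p of 0.1 to 0.3 and r = 0.005 this is 0.005 × 0.9 = 0.0045 down to 0.005 × 0.7 = 0.0035, or 0.35 to 0.45 percentage points.

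**The case against.** The strongest reply is that the protocol lists data to abstract and never states a scoring rule. How to treat an infant who dies before assessment may be settled in a statistical analysis plan that is not shown. This stands in part: counting the infant as event-free is an inference from the usual any-component reading. But the component list is fixed here, with thresholds and time windows, and a later plan would have to add to it.

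A second reply is that the numbers are tiny and the assumed rate may be too high. Eligibility excludes multiple gestations, major fetal anomalies, pre-existing diabetes, medicated hypertension and anticipated delivery before 34 weeks. Women with a 50 g result of 200 mg/dL or more are not randomized, and preterm delivery is among the reasons for which investigators may remove a participant. All of this stands. No material effect on the comparison between arms can be shown.

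Three stronger readings are tempting but unsupported:

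- *Every neonatal death is misclassified.* This is true only of deaths without another component. Glucose is due within the first hour, birth trauma is fixed at delivery, and bilirubin may be measured earlier when needed.
- *A testing strategy that moved deaths from before to after birth would look beneficial.* This is arithmetically possible, but nothing in the protocol suggests that either glucose test would do so.
- *The data are already in hand.* The abstraction list does not name death, and variables must be requested by the principal investigator.

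**Conclusion.** The gap is real, and it lies in what the protocol fixes, not in something left to a later document. The neonatal composite includes death before delivery and omits death after it. On the any-component reading, an infant who dies with no other component is grouped with the unaffected infants.

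The size is small: about 0.4 to 4.6 infants across 782 to 920, and at most about 0.5 percentage points on the composite rate, both under an assumed 0.5 to 5 deaths per 1,000. The conclusion does not depend on that range, because the argument concerns validity. It does depend on the scoring rule, which the protocol does not state. A reader might also infer that the primary endpoint is compromised. The protocol places this composite among several main outcomes and does not call it primary, so that inference goes too far.

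**What to change.** Three linked changes:

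1. In Data Collection Associated with Study Outcomes, replace component 3 with: *perinatal death: stillbirth, or death of a live-born infant before discharge from the birth hospitalization*.
2. In R3 Data Collection, name neonatal death as an item to be abstracted.
3. State that it is ascertained in the same way in both arms, for the entire maternal-infant cohort that the R3 team already follows, from the delivery and neonatal records. The laboratory part of the infant's record, now given as the source for the composite, should not be the only source.

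The Infant Status Form should not be the source. It is used as needed and only in the selected follow-up group. That group includes the mild-GDM designation, which exists only in Arm B, so relying on the form would miss infants outside the group and make ascertainment differ by arm.

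The cost is one extra abstraction item and a very slightly higher composite rate. Deaths after discharge would remain outside the component; that is the price of a single window that can be applied to every infant. No visit, test or sample size changes.

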### *Confidentiality*

The collection of sensitive information about participants is limited to the amount necessary to achieve the aims of the research. R3 computer-based files will only be made available to personnel involved in the study with access privileges and passwords. Prior to accessing any study-related information, personnel will be required to sign statements agreeing to protect the security and confidentiality of identifiable information.

## **Laboratory Procedures and Protocols**

### **Specimen Collection**

At Visit 1, one 5.0 mL gold top tube will be collected at the 1-hour time point for glucose testing.

At Visit 2, three 5.0 mL gold top tubes and one 3.5 mL lavender top tube will be collected at the fasting time point for fasting glucose, lipid panel, insulin, and high-sensitivity C-reactive peptide (hsCRP) testing. One 5.0 mL gold top tube will then be collected at each hourly time point (1 and 2 hours for the 75 g OGTT; 1, 2, and 3 hours for the 100 g OGTT) for glucose testing.

At delivery, one 3.5 mL gold top tube, one 5.0 mL lavender top tube, and one 5.0 mL gold top tube will be collected, in that specific order.

At Visit 3, three 5.0 mL gold top tubes and one 3.5 mL lavender top tube will be collected at the fasting time point for fasting glucose, lipid panel, insulin, hemoglobin A1c, and high-sensitivity C-reactive peptide (hsCRP) testing. One 5.0 mL gold top tube will then be collected at each hourly time point (1 and 2 hours for the 75 g OGTT).

For Visits 2 and 3 occurring on Saturdays, one extra 3.5 mL lavender top tube will be drawn at fasting.

*See Page 63 for Specimen and Laboratory Flow Chart.*

### **Laboratory Processing and Long-Term Specimen Storage**

All samples will be processed at the UPMC Clinical Laboratory Building with the exception of specimens collected at delivery, which will be processed by the MWH OSPU team.

All glucose tests, lipid panels, and high-sensitivity C-reactive peptide tests will be run at the UPMC Automated Testing Lab. The UPMC CLB will also run insulin tests at the Immunoserology Lab, and hemoglobin A1c at the Special Chemistry Lab.

Non-esterified free fatty acids, adiponectin, and leptin will be analyzed at the UPMC CLB or Indiana University Metabolic Lab (TBD).

All plasma and serum aliquots will be stored long-term at the Magee-Womens Research Institute.

### *Visit 1 Laboratory Procedures*

The 50 g 1-hour glucose specimen and a completed research requisition (see [Appendix C](#)) will be sent from MWH to the UPMC Clinical Laboratory Building (CLB Station #350) via pneumatic tube for processing. The CLB will process the glucose testing. Results will then be faxed to study staff within 1 business day. Specimens from Visit 1 will not be banked in long-term storage.

### *Visit 2 Laboratory Procedures*

The fasting specimens and corresponding completed research requisition will be sent from MWH to the UPMC CLB (Station #350) via pneumatic tube for processing. The CLB will process the fasting glucose, insulin, lipid panel, and hsCRP. The additional two or three hourly glucose specimens will also be sent to the CLB with corresponding completed research requisitions by pneumatic tube. All results will be faxed to study staff within 1 or 2 business days. Fasting adiponectin, leptin, and non-esterified fatty acids will be processed at a separate time, after all participants complete their Visit 2.

Study staff will retrieve an extra gold top tube and lavender top tube directly from the automated testing line at the Automated Testing Lab on the 5th floor of the CLB. CLB staff will centrifuge the tubes and store them until they are retrieved by study staff. These residual specimens will be retrieved by scanning the tube labels printed by CLB staff, sending them to the automated testing line.

Once tubes are processed and received, study staff will aliquot the plasma or serum from each specimen into cryovials and temporarily freeze (-20°C) and store them in the Palmer Lab (Room 3027) freezer. Total aliquots to be frozen in cryovials include: 4 fasting serums, 2 fasting plasmas, and 1 serum aliquot from each hourly glucose specimen, of 1 mL each. If the participant does not consent to banking of specimens for future research tests, study staff will only prepare two 1 mL fasting serum aliquots for cytokine analyses.

Study staff will prepare labels for each cryovial, which specify the participant's study ID, blood draw date and time, date and time of freezing, study arm, specimen type (serum or plasma), study arm, and numerical order within the batch. After each sample is aliquoted, labeled, and frozen, study staff will complete a specimen collection record to log all prepared samples, noting if there will be fewer samples or less volume in a specific aliquot than expected. The Palmer Lab (Room 3027) will temporarily hold frozen specimens in labeled boxes provided by this study.

For long-term storage, study staff will compile specimen collection records, label specimen boxes with study and PI information, and transport the specimen boxes from the Palmer Lab to the Magee-Womens Research Institute (MWRI) within an insulated box of dry ice (to be provided by the CTRC). Study staff have badge access to the MWRI lab where study specimens will be stored. One freezer with specimens is located on the 5th floor of MWRI, where lab benches may be used by study staff to prepare specimen boxes for storage.

Specimen maps will be prepared, with boxes placed and mapped by rows and columns with alphanumerical identification. Specimen collection records will be compiled, specimen maps updated and organized by study staff at each transfer, and all records will be kept in binders in the study office.

Separate boxes are required for each of the following: fasting serum for cytokine analysis, fasting serum, fasting plasma, 1-hour serum, 2-hour serum, and 3-hour serum. Samples will be transferred between lab bench and freezer on dry ice during the entire process. Study staff will organize fasting serums to be used for cytokine analysis into two groups: participants who completed the study at delivery, and participants selected to return for the 12-month postpartum follow-up at Visit 3. All remaining samples will be frozen (-80°C) and stored long-term at MWRI.

### *Cord Blood Laboratory Procedures*

Venous umbilical cord blood will be collected at delivery by OSPU staff for the analysis of C-peptide. Cord blood procurement supplies will be provided on an ongoing basis to the OSPU team, to include 5.0 mL gold top tubes, 3.5 mL gold top tubes, 2 mL cryovial tubes, blank cryovial labels, and labeled specimen boxes for storage. Each month, study staff will provide the OSPU staff with an updated list of expected participant deliveries for the upcoming month and prepared research requisitions for each participant.

When a study participant delivers, the OSPU staff will obtain cord blood samples with the kit provided, and enter specimen and collection information (Cord Blood Collection form) into the study database at the delivery time point. 2 plasma aliquots and 2 serum aliquots of 1 mL each will be collected and banked from the delivery specimens.

### *Visit 3 Laboratory Procedures*

The fasting specimens and corresponding completed research requisition will be sent from MWH to the UPMC CLB (Station #350) via pneumatic tube for processing. The CLB will process the fasting glucose, insulin, lipid panel, hsCRP, and A1c. The additional two hourly glucose specimens will also be sent to the CLB with corresponding completed research requisitions by pneumatic tube. All results will be faxed to study staff within 1 or 2 business days. Fasting adiponectin, leptin, and non-esterified fatty acids will be processed at a separate time, after all participants complete their Visit 3.

Study staff will retrieve the lavender top from the Special Chemistry lab on the 3rd floor of the CLB, after it has been used for A1c testing. This tube will be taken to the 5th floor Automated Testing Lab and centrifuged there. Study staff will also retrieve an extra gold top tube directly from the automated testing line at the Automated Testing Lab on the 5th floor of the CLB. CLB staff will centrifuge the tubes and store them until they are retrieved by study staff. These residual specimens will be retrieved by scanning the tube labels printed by CLB staff, sending them to the automated testing line.

Once tubes are processed and received, study staff will aliquot the plasma or serum from each specimen into cryovials and temporarily freeze (-20°C) and store them in the Palmer Lab (Room 3027) freezer. Total aliquots to be frozen in cryovials include: 4 fasting serums, 2 fasting plasmas, and 1 serum aliquot from each hourly glucose specimen, of 1 mL each.

Study staff will prepare labels for each cryovial, which specify the participant's study ID, blood draw date and time, date and time of freezing, study arm, specimen type (serum or plasma), and numerical order within the batch. After each sample is aliquoted, labeled, and frozen, study staff will complete a specimen collection record to log all prepared samples, noting if there will be fewer samples or less volume in a specific aliquot than expected. The Palmer Lab (Room 3027) will temporarily hold frozen specimens in labeled boxes provided by this study.

For long-term storage, study staff will compile specimen collection records, label specimen boxes with study and PI information, and transport the specimen boxes from the Palmer Lab to the Magee-Womens Research Institute (MWRI) within an insulated box of dry ice (to be provided by the CTRC). Study staff have badge access to the MWRI lab where study specimens will be stored. One freezer with specimens is located on the 5th floor of MWRI, where lab benches may be used by study staff to prepare specimen boxes for storage.

Specimen maps will be prepared, with boxes placed and mapped by rows and columns with alphanumerical identification. Specimen collection records will be compiled, specimen maps

updated and organized by study staff at each transfer, and all records will be kept in binders in the study office.

Separate boxes are required for each of the following: fasting serum for cytokine analysis, fasting serum, fasting plasma, 1-hour serum, and 2-hour serum. Samples will be transferred between lab bench and freezer on dry ice during the entire process. All samples will be frozen (-80°C) and stored long-term at MWRI.

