## **Randomization Procedures**

If the participant's 50 g GCT is less than 200 mg/dL, they are randomized to Arm A (75 g OGTT) or Arm B (100 g OGTT) by the randomization form. Once the glucose value from the 50 g GCT is entered and submitted into the database, study staff will open the randomization form in the database. The randomization form displays a "button", which will then be clicked to randomize the participant to Arm A or Arm B. All baseline measures must be completed and entered into the database and Visit 1 closed out before randomization can be completed. Study participants are to remain blinded to their randomized study arm until they arrive at the MWH CTSC for their Visit 2. When Visit 2 is scheduled, participants will be told that the randomization visit will take approximately 3.5 hours so as not to unblind them. The rationale for blinding participants to their study arm is preventing dropout based on the knowledge that they have been randomized to the longer test (i.e., 3 hour 100 g OGTT).

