## **Blinding**

Providers are blinded to which test their patient completed and the patient's numerical test results. Study staff will notify providers as to whether or not their patient has GDM; they will not be told the specific glucose values. Providers will administer care based on the reported diagnoses. Study investigators, including the PI, will remain blinded to the randomization schema and study outcomes until the completion of the study. The PI or co-investigators will only be unblinded in the following cases:

- 50 g glucose value of  $\geq 200$  mg/dL
- 100 g OGTT fasting value  $> 105$  mg/dL or 2 hour value  $> 200$  mg/dL, if 50 g GCT  $> 130$  mg/dL
- Any severe adverse event that warrants further medical intervention
- Symptomatic reactive hypoglycemia ( $< 55$  mg/dL)

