#### *Manual Data Entry*

Data will be entered on PCs, laptops, and tablets; this allows for mobile computing and better functionality. Study personnel are assigned unique login credentials to access only the data they are permitted to manage. Only designated study staff will have access to the database (including participant's personal information); the PI will have limited access to the database to prevent unblinding.

Before beginning study procedures where data collection and tracking are involved, study staff will log onto the device they are using through a secure web server. An additional log-in and password is then required to access the database. Once the screening process has been started in the database, participant ID numbers are generated and data capture and tracking begins.

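### Visit 2 and Visit 3 cryovial labels carry the study arm, and nothing in the manual masks it before the deferred adiponectin, leptin and fatty-acid assays

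*Protocol*

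**What the plan says.** Two sections of the Protocol (the manual of procedures) fix the label content. For Visit 3, the Visit 3 Laboratory Procedures section lists study ID and draw date and time, followed by "date and time of freezing, study arm, specimen type (serum or plasma") and the vial's place in its batch. For Visit 2, the corresponding section gives the same list with the arm entered twice: "date and time of freezing, study arm, specimen type (serum or plasma), study arm, and numerical order within the batch". The arm is the randomized allocation; under Randomization Procedures women are "randomized to Arm A (75 g OGTT) or Arm B (100 g OGTT").

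On the assays, the section on laboratory processing and storage states: "Non-esterified free fatty acids, adiponectin, and leptin will be analyzed at the UPMC CLB or Indiana University Metabolic Lab (TBD"). The Visit 2 and Visit 3 procedures defer these assays until all participants have completed the visit concerned. The method entries for the three analytes under Clinical Laboratory Protocols are still to be determined.

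On blinding, the Blinding section states: "Study investigators, including the PI, will remain blinded to the randomization schema and study outcomes until the completion of the study". It lists four exceptions, none of which concerns specimens. The Manual Data Entry section adds that "the PI will have limited access to the database to prevent unblinding".

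**The concern.** The manual protects the allocation in the database but prints it on the tube. A laboratory measurement involves some human judgement, such as whether to repeat a run or exclude a poor sample. The usual safeguard is that the person making that judgement cannot see the arm. If the arm stays on the vial, a between-arm comparison of adiponectin, leptin or fatty acids rests on results obtained without that safeguard. A reader of the results could raise this, and the manual as written would give no answer. The arm also travels with the frozen vials to any later user of the bank.

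**Working it through.** No arithmetic bears on this point. The check is whether the arm is on the vials that are assayed, whether it is masked anywhere, whether it has a use there, and at which visit it could matter.

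1. **Which vials carry the arm.** The label instruction covers each cryovial prepared at Visit 2 and at Visit 3. Saturday samples are processed in the usual way, so they presumably follow the same rule. Visit 1 samples are not banked. For cord blood the manual mentions only blank labels and does not give their content. The finding is therefore confined to Visit 2 and Visit 3 vials.

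2. **Which vials are assayed.** The three analytes are measured in fasting serum. The storage instructions under the Visit 2 and Visit 3 laboratory procedures put the fasting serum for cytokine analysis in its own boxes. Plasma and hourly serum carry the arm too but do not feed these assays.

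3. **Whether the arm is masked before assay.** The sections on labelling, storage, transfer and assay mention no coding, relabelling or arm-free run list.

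4. **Whether the arm has a handling use.** At Visit 3 every selected woman is asked to take the same 75 g test, or gives only a fasting sample if she already has a diagnosis of prediabetes or diabetes. That exception does not depend on arm, and the aliquot plan is the same in both arms: 4 fasting serum, 2 fasting plasma and 1 serum from each of 2 hourly draws, so 4 + 2 + 2 = 8 vials. At Visit 2 the fasting plan is again 4 + 2 = 6 vials in either arm. Only the hourly vials differ, with 2 for the 75 g test and 3 for the 100 g test. Study ID, draw time and specimen type already distinguish the vials. The manual gives no reason for printing the arm, and its double listing at Visit 2 suggests that the wording was not checked.

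5. **Where it could matter.** The Visit 2 fasting sample must be drawn before the glucose drink. It therefore precedes the randomized test and any diagnosis or treatment that follows, and serves in effect as a baseline value. The Visit 3 sample, about 12 months after delivery, comes after all of these and can be read as an outcome. Visibility of the arm matters mainly there.

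6. **Fit with the blinding rules.** The Blinding section covers providers and investigators, and participants are kept unaware of their arm until they arrive for Visit 2. Laboratory personnel and study staff are not mentioned. The label therefore contradicts no stated rule, but it works against the purpose of the Blinding and Manual Data Entry provisions.

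**The case against.** The strongest reply is that nothing has been breached. Study staff do the aliquoting, labelling, boxing and transport, and they already know the arm: they run the randomization form and confirm the assignment before giving the drink. A reader might infer that the labels unblind investigators. The document does not support this, because it has no investigator handling vials. A reader might also infer that technicians will accept or reject results with the arm in view. That goes beyond the text: the assay methods and laboratory are undecided, and the manual describes no rules for repeats or rejections. It also does not say whether the label prints a letter or a glucose dose, or in what form vials will reach the laboratory.

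Two further points are fair. At Visit 2 the 3-hour serum exists only in the 100 g arm, so those vials reveal the arm whatever the label says. And adiponectin, leptin and fatty acids are absent from the section on data collection for the main outcomes, which concerns birth weight, cesarean delivery, and maternal and neonatal composites taken from records.

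All of this stands, and it limits the point. It does not remove it. The 3-hour vials are not used for the three assays and are boxed separately, and no Visit 3 vial reveals the arm except through its label. That staff know the arm is no reason to pass it to a laboratory that has no stated need for it.

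**Conclusion.** The point holds as a minor one. As written, the manual discloses the allocation to whoever runs the adiponectin, leptin and fatty-acid assays, for no stated purpose. The consequence lies mainly with the Visit 3 fasting serum and is much weaker for the Visit 2 fasting serum. It is neither a breach of a laboratory-blinding rule nor a threat to the main outcomes. Any bias is probably small, and the document gives nothing from which to size it.

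This rests on two assumptions: that vials reach the assay laboratory under the labels described, and that no separate laboratory instruction outside this manual already masks them. If either is wrong, only the wording of the manual needs correcting.

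**What to change.** Delete the study arm from the label content in the Visit 3 and Visit 2 Laboratory Procedures. Identify each vial by study ID, visit, time point, specimen type and aliquot number.

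For vials already frozen, over-label the separately boxed cytokine aliquots, or transfer them under coded labels with a run list that omits the arm. A run list alone is not enough if the printed arm can still be read on the tube. Give priority to the Visit 3 set. Add a sentence to the section on laboratory processing and storage stating that assay personnel work without knowledge of arm and that the data center links results to arm by study ID.

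The cost is a change of label template and some staff time to over-label one existing set of aliquots. No visit, sample or assay is added, and the analysis does not change.
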